8.1.3 Other Secondary

The other secondary efficacy endpoints for this study are as follows:

- Change from baseline in worst leg pain score at each time point
- Change from baseline in worst low back pain score at each time point
- Change from baseline in ODI score at each time point
- Percentage of subjects with negative SLR test
- Percentage of subjects without hypoesthesia, muscle weakness or hyporeflexia
- Patient Global Impression of Change (PGIC) score at each time point
- Clinical Global Impression of Change (CGIC) score at each time point
- Change from baseline in 36-item Short Form Health Survey (SF-36) scores at each time point
- EuroQol Group 5-Dimension Quality of Life instrument, 5-level version (EQ-5D-5L) quality of life (QOL) score and VAS score at Week 13 and Week 52
- Work Productivity and Activity Impairment Questionnaire (WPAI) score at Week 13 and Week 52
- Incidence and amount of rescue medication use over 13 weeks
- Change from baseline in amount of rescue medication use at each time point
- Cumulative distribution of percentage change from baseline in worst leg pain score at Week 13 and Week 52

- Cumulative distribution of percentage change from baseline in ODI score at Week 13 and Week 52
- Responder rate by composite definition^{*1} at Week 13
- Change from baseline in intervertebral disc volume at Week 13 and Week 52
- Change from baseline in herniation volume at Week 13 and Week 52
- Incidence of post-treatment surgery for LDH at the same level of investigational product injection
- Number of subjects with recurrence of LDH^{*2} at Week 52

*1 A subject who meets all 4 criteria below (A, B, C, and D) as assessed at Week 13:

- A. A reduction of 30% in worst leg pain score during the past 24 hours assessed by VAS from baseline to Week 13;
- B. Improvement of 30% in ODI score from baseline to Week 13;
- C. Maintenance or improvement of neurologic status (motor, sensory, reflexes) from baseline to Week 13; and
- D. No “Treatment Failure”

“Treatment Failure” is defined as a subject to whom any of the conditions shown below become applicable until Week 13 after investigational product injection:

- i. Use of additional medication/therapy to treat TEAEs or complications associated with LDH
 - New prohibited medications used for more than 7 days;
 - Increase of restricted medications used for more than 7 days;
 - Use of new prohibited therapies; or
 - Increase in frequency or intensity of restricted therapies.

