11.6.3 Other Secondary

All endpoints, including the primary and key secondary endpoints, will be summarized by treatment group and by time point. The differences of other secondary endpoints between the SI-6603 and control groups will be analyzed at each time point as below. In addition, weekly pain intensity scores will be summarized by treatment group.

- A similar longitudinal analysis model will be used as described in the primary efficacy analysis for the analysis of change from baseline in pain intensity scores, function scores, QOL scores, and volumes, by including the corresponding baseline value as the fixed effect instead of the baseline worst leg pain score.
- Neurologic status as determined by neurological examinations will be analyzed with a logistic regression model. Baseline neurologic status and duration of leg pain will be included as covariates.
- For the global assessments of PGIC score and CGIC score, responder analysis with the two best categories as “responder” will be analyzed with a logistic regression model. Baseline worst leg pain score and duration of leg pain will be included as covariates.
- Scores on the WPAI will be analyzed with the analysis of covariance model including the baseline value and duration of leg pain as covariates.
- The incidence of rescue medication use will be analyzed with Fisher’s exact test, and the amount of rescue medication use and usage of concomitant medications for LDH will be analyzed with the Wilcoxon rank sum test.
- Cumulative distribution of percentage change from baseline in worst leg pain and ODI will be generated, and differences between the SI-6603 and control groups in the percentages of subjects experiencing a >30% and >50% improvement in worst leg pain score will be analyzed with Fisher’s exact test.
- For the analysis of the percentages of responders by composite definition, differences between the SI-6603 and control groups in the percentages of positive responders will be analyzed with a logistic regression model. Baseline worst leg pain score and duration of leg pain will be included as covariates.
- Time to post-treatment surgery for LDH will be evaluated by survival analysis using the log-rank test.

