2.6 Sample Size Determination

It is planned to enroll approximately 320 subjects, 160 in the SI-6603 group and 160 in the control group.

Sample size estimation is based on using the mean difference in the worst leg pain score change from baseline in the primary efficacy analysis. The following assumptions were made to compute the sample size:

- The 2-sample t-test comparing the group means of the change from baseline was used. (The 2-sample t-test approximates the test of the null hypothesis based on the repeated measures model that will be used in the primary efficacy analysis.)
- Treatment difference between SI-6603 and control groups of 12 mm
- Common standard deviation (SD) of 30 mm
- Dropout rate of 15%
- Power of 90%
- Two-sided significance level of 5%

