7.2 Efficacy Variables

The primary efficacy outcome is the change from baseline in the weekly averages of the VAS worst leg pain assessed at Weeks 1, 2, 4, 6, 13, 26, 39, and 52. Baseline is defined as the average of the 7 daily worst pain measures leading up to the randomization visit.

Key secondary outcomes include:

- Change from baseline to Week 13 in herniation volume
- Change from baseline to Week 13 in ODI score
- Change from baseline to Week 52 in average worst leg pain score during the past 24 hours over the previous 7 days, as assessed by 100 mm VAS.

Supportive outcomes include:

- Change from baseline in worst leg pain score at each time point
- Change from baseline in worst back pain score at each time point
- Change from baseline in ODI score at each time point
- Percentage of subjects with negative SLR test at each time point
- Percentage of subjects without hypoesthesia, muscle weakness or hyporeflexia at each time point
- Patient Global Impression of Change (PGIC) score at each time point
- Clinical Global Impression of Change (CGIC) score at each time point
- Change from baseline in SF-36 scores at each time point
- EQ-5D-5L (EuroQol Group 5-Dimension Quality of Life instrument, 5-level version) quality of life (QOL) score and VAS score at Week 13 and Week 52
- WPAI score at Week 13 and Week 52
- Incidence and amount of rescue medication use over 13 weeks
- Change from baseline in amount of rescue medication use at each time point
- Cumulative distribution of percentage change from baseline in worst leg pain score at Week 13 and Week 52
- Cumulative distribution of percentage change from baseline in ODI score at Week 13 and Week 52
- Responder rate by composite definition at Week 13
- Change from baseline in intervertebral disc volume at Week 13 and Week 52
- Change from baseline in herniation volume at Week 13 and Week 52
- Incidence of post-treatment surgery for LDH at the same level of investigational product injection
- Number of subjects with recurrence of LDH at Week 52

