7.3.3.3 Other Secondary

All endpoints, including the primary and key secondary endpoints, will be summarized by treatment group and by time point. The differences of other secondary endpoints between the SI-6603 and control groups will be analyzed at each time point they are collected as below.

- A similar longitudinal analysis model will be used as described in the primary efficacy analysis for the analysis of change from baseline in pain intensity scores, function scores, QOL scores, and volumes (intervertebral disc and herniation), by including the corresponding baseline value as the fixed effect instead of the baseline worst leg pain score.
- Percentage change from baseline in intervertebral disc and herniation volumes will be summarized in a line graph with error bars.
- Neurologic status as determined by neurological examinations will be compared between treatments with a difference in proportions Z test. In the case of low counts (<5 expected in a cell), a Fisher's exact test will be used. Outcomes will include SLR test, sensation, muscle strength, and deep tendon reflex. Counts and percentages in each category will be presented along with 95% confidence intervals, the difference in the percentages and its 95% Wald CI. Percentages will be reported out of non-missing values.
- For the global assessments of PGIC score and CGIC score, responder analysis with the two best categories as "responder" will be compared between treatments with a difference in proportions Z test. In the case of low counts (<5 expected in a cell), a Fisher's exact test will be used. Counts and percentages in each category for the PGIC and CGIC will be presented as well as the responder/non-responder counts and percentages along with 95% confidence intervals, the difference in the percentages of responders and its 95% Wald CI. Subjects with missing values will be considered non-responders.
- Scores on the WPAI will be analyzed with the analysis of covariance model including the baseline value and duration of leg pain as covariates.
- The incidence of rescue medication use will be compared between treatments with a difference in proportions Z test. In the case of low counts (<5 expected in a cell), a Fisher's exact test will be used. The amount of rescue medication use will be analyzed with the Wilcoxon rank sum test.

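### PGIC and CGIC are compared between arms only at a two-best-category cut; adding an ordinal analysis with a stated missing-data rule would be a cheap gain in precision

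*SAP*

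**What the plan says.** The endpoints are listed as scores: "Patient Global Impression of Change (PGIC) score at each time point" (SAP 7.2) and "Clinical Global Impression of Change (CGIC) score at each time point" (Protocol 8.1.3). Ratings are taken at Weeks 2, 4, 6, 13, 26, 39 and 52 and at discontinuation (Protocol 9.5.5 and 9.5.6).

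SAP 7.3.3.3 reduces them to yes or no: "For the global assessments of PGIC score and CGIC score, responder analysis with the two best categories as" responder. The proportions "will be compared between treatments with a difference in proportions Z test", with Fisher's exact test when expected counts are low, and the difference is given with a Wald interval. The full distribution is descriptive: "Counts and percentages in each category for the PGIC and CGIC will be presented". On missing data: "Subjects with missing values will be considered non-responders".

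The longitudinal model in the same section covers pain, function, quality of life and volumes, but not the global ratings. Protocol 11.6.3 makes the same cut but analyses it by logistic regression: "Baseline worst leg pain score and duration of leg pain will be included as covariates". The SAP drops those covariates, and SAP 11 does not list that change.

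SAP 7.3.4 places PGIC and CGIC outside the gatekeeping sequence. P-values for such endpoints may be reported, but none counts as statistically significant.

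**The concern.** A two-category cut ignores every shift that does not cross it. A move from worse to no change, from no change to slight improvement, or between the two best categories adds nothing to the comparison. Elsewhere in SAP 7.3.3.3 more of the scale is kept: a rank test for the amount of rescue medication, analysis of covariance for WPAI, and cumulative distributions beside the 30% and 50% cuts for leg pain. The global ratings have no such companion, and neither document gives a reason for the cut.

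These ratings help a reader judge whether a mean VAS difference matters to patients and to blinded investigators. What is at stake is how precisely the arms are compared on them.

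**Working it through.** **1. The plan's own figure.** SAP 2.6 has "Treatment difference between SI-6603 and control groups of 12 mm", SD 30 mm, 90% power, two-sided 5% and 15% dropout. n per arm = 2 × (1.960 + 1.282)² × (30/12)² = 131.4, so 132 (133 with the t distribution). Dividing by 0.85 gives 156 (157), against 160 planned. The figure reproduces.

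**2. Inputs for the global ratings.**
- From the documents: 160 per arm; 160 × 0.85 = 136 observed per arm; two-sided 5%.
- Assumed: a latent normal shift d = 12/30 = 0.40, which is the VAS value; seven categories; control responder rate r of 20-60%; control non-responders split 5/10/15/30/40% from worst upward, and responders 60/40%. Two other splits of the non-responders move the loss by less than one point.

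**3. Formulas.** Active responder rate = Φ(Φ⁻¹(r) + 0.40). Power of the cut = Φ[(difference − 1.96 × SE₀)/SE₁], where SE₀ is the pooled and SE₁ the unpooled standard error. The ordinal test is the tie-corrected Wilcoxon test, based on θ = P(active rated better) + ½P(tie).

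Example, r = 30%:
- Active rate = Φ(−0.524 + 0.40) = 45.0%.
- SE₀ = √(2 × 0.375 × 0.625/136) = 0.0587; SE₁ = 0.0580.
- Power of the cut = Φ[(0.1505 − 0.1151)/0.0580] = 72.9%.
- Rank test: θ = 0.607, standard error about 0.034, power 88.2%.

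**4. Observed ratings, 136 per arm.**

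| Control rate | Active rate | Two-best cut | Rank test | Loss (points) |
|---|---|---|---|---|
| 20% | 32.9% | 67.8% | 88.2% | 20.4 |
| 30% | 45.0% | 72.9% | 88.2% | 15.3 |
| 40% | 55.8% | 74.6% | 87.8% | 13.3 |
| 50% | 65.5% | 74.0% | 87.3% | 13.3 |
| 60% | 74.3% | 71.3% | 86.4% | 15.1 |

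Losses are from unrounded powers. Simulation of the same settings gives 69-74% for the cut and 86-88% for the rank test. As relative information, at r = 30% the ratio is [(0.61 + 1.96)/(1.185 + 1.96)]² = 0.67, so the cut uses about two thirds of the information.

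**5. Sensitivity of the loss.**
- Five categories: 13-19 points.
- 160 evaluable per arm: 11-18 points.
- Logistic shift, odds ratio exp(0.4π/√3) = 2.07, 136 per arm: 7.5-17 points. With 160 per arm as well: 6-14 points.
- Shift of 0.3 SD (r = 20-50%): 14-22 points. Shift of 0.2 SD: 8-13 points.
- Control rate of 10%: 31-33 points.

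**6. Missing ratings.** All 160 per arm analysed, 15% missing in each arm, 100,000 simulated trials per row. The cut counts missing as non-responder, as the SAP does.

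| Control rate | Two-best cut | Ordinal, missing = no change | Gain | Ordinal, missing = worst category | Gain |
|---|---|---|---|---|---|
| 20% | 65.8% | 85.0% | 19.2 | 69.6% | 3.7 |
| 30% | 69.4% | 84.1% | 14.7 | 69.6% | 0.2 |
| 40% | 68.2% | 82.3% | 14.1 | 68.8% | 0.6 |
| 50% | 66.1% | 80.3% | 14.2 | 67.8% | 1.7 |
| 60% | 59.2% | 77.2% | 18.0 | 66.1% | 6.9 |

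If missing is ranked below every observed category, the difference is −1.5 to +2.3 points at control rates of 20-50%. The gain therefore depends on the missing-data rule.

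**7. Opposing shifts.** Suppose responders rise from 35% to 50% while worse ratings rise from 12% to 25%, with 136 per arm. The cut has 71% power. The rank test has about 11-16%, depending on how the remaining ratings are spread, because it nets the two movements.

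**The case against.** The case for leaving the plan alone is strong in four respects.

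- **No formal claim depends on this power.** SAP 7.3.4 bars any declaration of significance on these endpoints. Benefit is tested on leg pain, herniation volume and ODI by repeated-measures models. This stands.
- **The effect size is borrowed.** A reader might infer that PGIC and CGIC lose power under the trial's own planning effect. The documents do not support that: 12 mm over 30 mm belongs to VAS worst leg pain, so the loss is only a conditional range.
- **Harm is not hidden.** A reader might infer that a shift toward worse ratings would go unseen. The category counts by arm would show it. SAP 8.2 also reports treatment-emergent back-pain and leg-pain events with exact 95% intervals, and worst back pain has its own longitudinal analysis. What is missing is only a between-arm comparison that uses those categories.
- **The cut is legitimate.** It is prespecified in both documents, and a responder difference with its interval is easy to read. A reader might infer that an ordinal analysis should replace it. Step 7 argues against that, since a single common odds ratio can conceal opposing shifts. An analysis of observed ratings alone would also drop subjects who withdrew for poor response or adverse events, so it should not be the main ordinal run.

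What survives is narrower: the order of the categories is collected, tabulated and then used in no comparison, and adding one is cheap.

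**Conclusion.** The point holds as an optional improvement, not as an error. The two-best-category cut is the only planned between-arm comparison of PGIC and CGIC. Under the assumptions of step 2 it gives up about 13-20 points of power relative to an ordinal test, or about 7-18 points with a logistic shift or 160 evaluable per arm. With missing ratings set to no change the ordinal gain is about 14-19 points. With missing ratings placed in the worst category it is 0-4 points up to a 50% control rate and 7 points at 60%.

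The practical meaning is a more precise supportive estimate. It would go too far to infer that the efficacy conclusions are weakened or that the responder analysis is invalid: the primary and key secondary tests do not involve these ratings.

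**What to change.** In SAP 7.3.3.3:

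1. Keep the responder comparison with its difference and confidence interval as written.
2. Add, at each visit and for each scale, a supportive proportional-odds analysis of all categories with treatment, baseline worst leg pain and duration of leg pain, the covariates of Protocol 11.6.3. Report the common odds ratio with its 95% interval.
3. Fix the missing-data rule before unblinding: all mITT subjects, with missing ratings set to no change. Add one sensitivity run on observed ratings and one with missing ratings in the worst category. State the category list, so that no change is defined.
4. Check proportional odds and report cumulative odds ratios by cut, so that opposing movements in the best and worst categories remain visible.
5. Note in SAP 11 that the protocol's adjusted logistic regression became an unadjusted comparison of proportions, or restore it.

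The cost is SAP wording and one extra model per scale and visit (2 × 7 = 14 main fits), on data already collected, plus the sensitivity runs. The downsides are an effect measure that is harder to read than a percentage and a model assumption that must be checked.

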9.5.7 Work Productivity and Activity Impairment

- Assessment Points: Week 0, 13, and 52, and discontinuation visit
- Item: Work Productivity and Activity Impairment Questionnaire: Pain related to Lumbo-sacral Radiculopathy V1.0 (WPAI-PLR, referred to as WPAI)
- Method: Investigators will have subjects answer the WPAI questionnaire at each listed visit.

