7. EFFICACY EVALUATION

7.1 Overview of Efficacy Analysis Issues

7.1.1 Handling of Dropouts or Missing Data

For the efficacy analysis based on repeated-measures models of continuous endpoints, missing data will be implicitly handled via a mixed-effect model, without explicit imputation. Inferences based on this approach are unbiased under the assumption of missing at random (MAR), which is a weaker and more generally true assumption than missing completely at random (MCAR).

For the primary efficacy analysis, sensitivity analysis based on multiple imputation (MI) methods that changes imputation methods by missing pattern such as discontinuations due to AEs, lack of efficacy, and other will be performed for the mITT population.

For the analysis of percentages of positive responders by composite definition, no imputation will be performed. However, subjects will only be considered responders if they meet all criteria, thus, subjects with missing data and dropouts will implicitly be treated as non-responders.

No replacement of any missing data will be made for the safety analyses.

Additionally, see Section [7.3.2.1](#) for data handling regarding the VAS pain scores for the definition of a non-missing week and data censoring rules.

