7.1.2 Assessment Time Windows

All data collected during follow-up will be displayed and analyzed according to the actual visit that the data are assigned in the eCRF.

Study discontinuation visits will be assigned to the corresponding visit if it falls within the protocol window for that visit. For example, a discontinuation visit on day 100 would be assigned to Week 13 since it falls within the -7/+14 day window for Week 13.

However, if scheduled visit data are present, then the discontinuation visit data will not be used for that visit. This will be done on a parameter level and discontinuation visit values will not be assigned to visits where the assessment was not scheduled to be taken (For example, Week 4 does not have MRI, but the discontinuation visit does; even if the discontinuation visit falls in the Week 4 window, we would not assign the MRI findings to a Week 4 visit).

Unscheduled assessments (laboratory data, imaging findings or vital signs associated with non-protocol clinical visits or obtained in investigating or managing AEs) will be included in listings but not summaries of the data. Likewise, discontinuation visit data that do not fall within a protocol-defined window or fall within a window where

scheduled visit data are already present will not be summarized, but will appear in listings.

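### WPAI gets an ANCOVA at each visit with no missing-data rule, although the SAP already uses the longitudinal model for endpoints measured at the same two visits; the cost falls on the Week 52 comparison and is small

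*SAP*

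**What the plan says.** - **Model for WPAI.** SAP 7.3.3.3: "Scores on the WPAI will be analyzed with the analysis of covariance model including the baseline value and duration of leg pain as covariates". Protocol 11.6.3 has the same ANCOVA. The SAP section opens with: "The differences of other secondary endpoints between the SI-6603 and control groups will be analyzed at each time point they are collected as below". For WPAI that means one comparison at Week 13 and one at Week 52.
- **Visits.** Protocol 9.5.7 gives for WPAI: "Assessment Points: Week 0, 13, and 52, and discontinuation visit". Protocol 9.5.4 gives the same list for EQ-5D-5L.
- **Model for comparable endpoints.** The longitudinal-model bullet in SAP 7.3.3.3 covers "analysis of change from baseline in pain intensity scores, function scores, QOL scores, and volumes (intervertebral disc and herniation"). SAP 7.2 lists EQ-5D-5L as a "quality of life (QOL) score and VAS score at Week 13 and Week 52", so it falls under that bullet. SAP 7.3.3.1 applies the same model to herniation volume and notes that it has post-baseline data only at Weeks 13 and 52.
- **Missing data.** SAP 7.1.1: "For the efficacy analysis based on repeated-measures models of continuous endpoints, missing data will be implicitly handled via a mixed-effect model, without explicit imputation". The section also has rules for the primary multiple-imputation analysis, the composite responder and safety data. SAP 7.3.3.2 extends imputation to the key secondary endpoints. SAP 7.3.3.3 says how missing values are treated for PGIC, CGIC, neurologic status and percentage improvement in leg pain. None of these rules covers WPAI.
- **Discontinuation visits.** SAP 7.1.2: "Study discontinuation visits will be assigned to the corresponding visit if it falls within the protocol window for that visit". Discontinuation data outside a window are listed but not summarised.
- **Status.** WPAI is an other secondary endpoint and is not in the gatekeeping sequence of SAP 7.3.4.

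**The concern.** Two instruments completed at the same visits by the same subjects are analysed by different models, and the documents give no reason. Having only two post-baseline visits is not the reason, since herniation volume has only two and gets the longitudinal model.

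The practical effect is at Week 52. The Week 13 window ends on Day 106 (92 + 14) and the Week 52 window opens on Day 351 (365 − 14). For a subject who leaves between those days, the Week 13 WPAI is the last value that can enter an analysis. The ANCOVA at Week 52 ignores it; the longitudinal model would use it. Protocol 5.1 provides for withdrawal after poor response and after surgery for the herniation at any time, so leavers may not resemble those who stay. At stake are some precision at Week 52 and, if the arms lose subjects differently, some bias in the WPAI treatment difference.

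**Working it through.** **Inputs from the documents.** 160 subjects per arm, 1:1 allocation, 15% drop-out, difference 12 mm, SD 30 mm, 90% power, two-sided 5% (SAP 2.5 and 2.6). The documents give no planning figure for WPAI.

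**The plan's own figure.** The normal approximation gives 132 per arm and the exact two-sample t-test 133. Dividing by 0.85 gives 156 and 157 per arm, 312 to 314 in total, against a planned 320. The plan's figure is reproduced. With 15% lost, 160 × 0.85 = 136 per arm remain at Week 52.

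**Assumptions not in the documents.** The Week 13–Week 52 correlation r, given the covariates in the model (0.3 to 0.8); the share of leavers who go after Week 13; the drop-out mechanisms; and a true effect of 12/30 = 0.4 SD, borrowed from the primary endpoint.

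**Precision.** With two visits and no return after drop-out, the variance of the Week 52 estimate from the longitudinal model, divided by that from the Week 52 ANCOVA, is 1 − r²(1 − n52/n13). Here n13 and n52 are the numbers per arm seen at each visit.

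- All leave after Week 13: n13 = 160, so 1 − 136/160 = 0.15.
- Half leave before Week 13: n13 = 148, so 1 − 136/148 = 0.081.

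| r | SE reduction, all leave after Week 13 | Effective n per arm (from 136) | SE reduction, half leave before Week 13 |
|---|---|---|---|
| 0.3 | 0.7% | 138 | 0.4% |
| 0.5 | 1.9% | 141 | 1.0% |
| 0.7 | 3.7% | 147 | 2.0% |
| 0.8 | 4.9% | 150 | 2.6% |

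For example, at r = 0.7 with all leaving after Week 13: 1 − 0.49 × 0.15 = 0.9265, square root 0.9625.

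**Bias under MAR.** Each scenario was simulated 4,000 times with 160 per arm and a 0.4 SD benefit at both visits. Where drop-out depends on outcome, its log-odds change by 1 per SD of the Week 13 value. Values stand for outcomes given the covariates. The entries are the bias of the Week 52 difference using only subjects seen at Week 52, in SD units; positive means the benefit is understated. Monte Carlo error is about 0.002.

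| Drop-out (control / SI-6603) | r = 0.3 | r = 0.5 | r = 0.7 |
|---|---|---|---|
| Same dependence, 15% / 15% | 0.004 | −0.001 | 0.001 |
| Same dependence, 20% / 10% | 0.027 | 0.039 | 0.054 |
| Dependence in control only, 15% / 15% | 0.039 | 0.065 | 0.092 |
| Dependence in control only, 20% / 10% | 0.053 | 0.089 | 0.124 |
| Opposite dependence, 15% / 15% (extreme) | 0.080 | 0.134 | 0.185 |

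The likelihood estimate that uses the Week 13 values stayed within 0.005 SD of the truth throughout. For scale, the standard error of the difference is √(2/136) = 0.12 SD.

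**The case against.** Baseline-adjusted ANCOVA is a recognised analysis, the protocol and the SAP agree on it, and nothing obliges two instruments with the same visits to share a model. It already adjusts for baseline WPAI and duration of leg pain, so drop-out that depends only on those and on arm is accommodated. WPAI carries no confirmatory claim. All of this stands, and it is why the point is minor.

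Four stronger readings are tempting, and the documents do not support them.

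- *The Week 52 difference is biased whenever drop-out depends on Week 13 status.* With the same dependence and the same 15% rate in both arms the bias is about zero. It needs a difference between arms, which withdrawal for poor response makes plausible in a sham-controlled trial but not certain.
- *The longitudinal model cures informative withdrawal.* It does so under MAR only. Withdrawal at surgery may reflect worsening after Week 13 that no scheduled WPAI records, and then both models can be biased. Subjects withdrawn for a block procedure before Week 13 will mostly have no Week 13 WPAI, so the model gains little from them.
- *All WPAI data from leavers are lost.* A discontinuation visit inside the Week 13 or Week 52 window is used when the scheduled value is absent.
- *The SAP prescribes a complete-case analysis.* It does not use those words. They follow from analysis at each collected time point, a model without a repeated-measures term, and the absence of any imputation rule.

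The precision gain also depends on the correlation after adjustment. If the raw correlation is 0.6 and each visit correlates 0.4 with baseline (both assumed), the adjusted value is (0.6 − 0.16)/(1 − 0.16) = 0.52. The gain at 15% drop-out with half leaving early is then about 1.1%.

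**Conclusion.** The point holds as a small and inexpensive improvement. The ANCOVA is an unexplained, weaker choice for Week 52 WPAI, and neither document says how missing WPAI values are handled. At the planned 15% drop-out, the longitudinal model would reduce the Week 52 standard error by about 0.4% to 5% for adjusted correlations of 0.3 to 0.8. Under MAR it would also remove a bias that arises only when the arms differ in drop-out rate or mechanism: about 0.03 to 0.12 SD in the moderate scenarios and up to 0.19 SD in the extreme one. The correlations and mechanisms are assumptions. Week 13 is hardly affected, because a subject lost before Week 13 has no later value to borrow from. Primary and key secondary conclusions are unaffected.

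**What to change.** In SAP 7.3.3.3, delete the WPAI ANCOVA bullet and add WPAI scores to the longitudinal-model bullet: change from baseline at Weeks 13 and 52, with baseline WPAI, treatment, time, treatment-by-time interaction and duration of leg pain. The missing-data statement in SAP 7.1.1 then applies to WPAI without further text. Because Protocol 11.6.3 also names ANCOVA, record the change in SAP section 11.

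If the sponsor has a reason to keep the ANCOVA, the minimum is one sentence giving that reason and one stating how missing WPAI values are handled.

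The cost is about two sentences. The two-visit model is already planned for EQ-5D-5L and the volumes, so little new programming is needed.
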